**HIV DRM testing:** We will conduct targeted HIV DRM testing at the Kisumu-based KEMRI-CDC HIV Research laboratory using consensus sequencing on all plasma samples which lack viral suppression, defined as VL  $\geq$  1000 copies/mL per national guidelines. “Targeted” DRM testing will include DRM testing for each child on the first detection of such a VL and in children newly initiating ART. Subsequent samples from the same child on the same ART regimen will not be routinely retested, since costs of repeat DRM testing outweigh detection of new DRMs. Since approximately 65% of children achieve viral suppression currently in the FACES-supported facilities, including the study facilities, i.e. 35% have viremia VL  $\geq$  1000 copies/mL, we anticipate conducting DRM testing in at least 100 samples in participants in the intervention arm over the course of this pilot study. Such plasma samples, once processed from whole blood within 6 hours of collection, will be transported from the local health facility to the KEMRI-CDC laboratory the same day.

To conduct the HIV DRM testing, we are partnering with KEMRI-CDC, which has extensive facilities, including the HIV Research Laboratory led by [name], a collaborator on this proposal, located immediately outside of Kisumu. The KEMRI-CDC HIV Research laboratory utilizes Applied Biosystems (ABI) 3130x/ Genetic Analyzers to conduct its HIV drug resistance testing on 0.5-1mL of plasma. These analyzers have all steps automated, from polymer loading to sample injection to data analysis. This laboratory utilizes an optimized in-house assay to detect reverse transcriptase- and PI-based mutations. This validated, assay is broadly sensitive in genotyping HIV-1 subgroups, detecting all mutations classified in the IAS-USA mutations list, and more sensitive than commercially available assays for mixed viral populations. The KEMRI-CDC in-house assay can run samples from plasma or DBS; the ability to also use DBS is a key asset for our study, in case adequate volume of plasma cannot be obtained from our younger study population. DBS samples will be prepared by spotting 100  $\mu$ L of whole blood onto each of the preprinted circles on the DBS paper, then dried overnight at the local health facility at ambient temperature, and then transport wrapped DBS cards the next day.

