To further analyze emerging DRM for DTG, we will follow participants longitudinally after they reach the study primary endpoint (of 12 months after enrollment) and follow their routine care VL patterns while on DTG via an observational extension of this project for up to 5 years. If VL $>200$  copies/mL is detected by reviewing routine care records, study staff will contact the participant for either additional blood collection or permission to use any stored sample for next-generation sequencing (NGS) and phenotyping. All samples with VL  $\geq$ 200 copies/ml will be tested by NGS using the Illumina MiSeq platform using Primer ID in [name] lab at Seattle Children's Research Institute in Seattle, WA (the children's hospital affiliated with the University of Washington). This NGS method will allow for detection of low-frequency drug resistance mutations (minority variants), which may be present at baseline and/or at time of viremia. Sequences will be analyzed for HIV drug resistance mutations using the Stanford HIV drug resistance database (HIVdb) genotypic resistance interpretation system, and drug resistance mutations will be reported at detection thresholds of 1%, 2%, 5%, 10%, and 20%. The results

will be returned to the facility staff. For phenotyping resistance patterns, [name] lab at the University of Washington will perform phenotypic resistance testing for those samples with relevant genotypic mutations. His lab requires two 2-mL cryovials of plasma, which will be collected at the time of blood collection for NGS sample collection. Neither validated NGS nor phenotypic resistance testing is currently available in Kenya, thus, requiring shipment of samples to the U.S. During this observational-only phase of the project, participants will continue to receive testing, treatment, and other procedures as part of routine care, according to the standard-of-care then; study staff will not be providing any interventions, but only collect blood samples and administer questionnaires every 6 months up to 5 years of follow-up. However, if any irregularities in routine care are noted in regards to treatment or monitoring by study staff during this observational-only phase, study staff will alert the health facilities for possible routine care interventions.

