## Procedures

**Blood sample collection:** For children in the intervention arm: blood samples will be collected every 3 months for POC VL testing and DRM testing per protocol for the first 12 months. For children in the control arm: blood samples will be collected per standard of care by non-study clinic staff per routine clinic schedule after study enrollment. Newly initiating children will undergo baseline VL and DRM testing as outlined above. After either intervention or control arm participants reach the primary endpoint of 12 months after enrollment, for the observational-only phase of this project, they may be followed every 6 months up to 5 years by routine clinic staff for VL monitoring; if VL $\geq$ 200, then study staff will request routine staff to share any leftover or stored plasma sample to obtain NGS genotyping and phenotyping. If no stored samples exist (for example, at the VL testing facility) or not in sufficient quantities, then the participant will be asked to return to the clinic for additional sample collection for NGS genotyping and phenotyping. Phlebotomy required for POC VL testing and DRM testing is also required for routine lab and viral load monitoring already a part of HIV care in Kenya. However, this will be more frequent than routine lab monitoring. Participants may experience some additional pain and anxiety due to this. This risk will be minimized by utilizing trained study nurses with experience collecting blood in children. Additionally, if the required 4ml of blood is not obtained, we will utilize dried blood spots which require less blood to reduce the need to perform additional phlebotomy. Once the testing for the study is completed, remaining samples will be stored in Kenya and later batch transported to the UW ICRC Laboratory Repository for storage for future studies.

**Blood sample storage and transfer:** Existing standards and best practices will be followed for blood sample storage and transfer. Greater details are found in the laboratory standard operating procedure.

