**Study Aim 2:** To estimate (**Aim 2a**) the effect of providing timely DRM results on viral suppression for intervention participants undergoing DRM, separately from the effect of POC alone, a secondary analysis will be performed with outcome of time to viral suppression. As in Aim 1, we will use a Cox model with primary predictor of intervention vs. control arm. To distinguish the effect of DRM results from that of POC VL testing, we will add a time-varying covariate which indicates, for each visit with a VL test, whether the clinician was notified of a positive DRM result since the child's prior VL test. If implemented as expected, all children without viral suppression will be provided DRM testing and providers notified of the results. This model will allow us to divide the estimated effect of the intervention between the effect of POC VL testing alone (on those who do not have DRM), and the effect of POC VL testing plus DRM testing for those who do undergo DRM testing. We will perform these Cox models both unadjusted and adjusted, accounting for other factors likely to affect viral suppression, particularly those that may vary at baseline in the intervention vs. control arms.

We will also describe the proportion of samples within the intervention arm that have any targeted DRMs by HIV drug classes, e.g. NRTIs, NNRTIs, and PIs. We will report the proportion of samples with each type of mutation detected by drug class, and further group these mutations into major and minor ones. For example, we will examine major mutations in M184V/I and K65R for NRTIs, K103N, Y181C, G190A, and V106M for NNRTIs, and V82A, I76V, 184V, L47A, L90M, M46I, and D30N for PIs; one or more of the NRTI and NNRTIs mutations alone accounted for 99% of the mutations detected among adults on 1st line ART from resource-limited settings with similar findings in small studies conducted with children, though the rates of PI-based mutations are increasing with more children on PI-based regimens. With 284 participants randomized to the intervention arm, we expect approx. 35% (100) to not achieve viral suppression at their 1st POC VL test and undergo DRM testing. With n=100, we will be able to estimate prevalence of DRMs to within +/- 5% to 10% of the 95% CIs. For example, for a class of DRMs with prevalence of 80%, we anticipate generating exact 95% CIs of 71.3%-87.0%; a less common DRM at 10% will generate 95% CIs of 5.1%-17.1%.

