We will use logistic regression models to identify risk factors associated with major and any DRMs. Potential risk factors of interest include individual-level (age, sex, duration on ART, prior antiretroviral exposure, prior viral suppression patterns, WHO clinical stage), clinical parameters (such as weight- or height-for-age), immunological status, family-level, HIV status of caregivers, socioeconomic status, and facility-level factors, such as volume of patients and urban/rural location. Covariates with p<0.20 in univariate analyses will be included in the multivariate models. We will also consider including interaction terms for any suspected effect modifiers such as age group of the child. The above analytic approaches will be taken for analyzing data from the NGS genotyping and phenotyping; in addition to descriptively generating the

patterns and distribution of NGS-detected DRM, including for minority variants and for mutations relevant to DTG, we will also compare them to the results obtained via CS when concurrent results are available.

To evaluate **Aim 2b**, CS and OLA simple-based DRM testing (Aim 4): To evaluate the test performance of OLA Simple (Aim 4a), we will compare test results for each codon from the OLA Simple test against a composite “gold standard” constructed from CS and Illumina sequencing (the latter performed on samples that are negative for DRMs by CS), stratified by retro- or prospective testing. We will calculate sensitivity, specificity, and positive and negative predictive values for the detection of DRMs per codon, organized by drug classes, for the OLA Simple. The above are the fundamental metrics the WHO, for example, considers in its prequalification application for in-vitro diagnostic and laboratory technologies approvals, achieving sensitivity and specificity >90% would demonstrate high test performance.

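### The plan does not fix the unit of analysis for the NGS resistance data: a child can contribute several sequences, the outcome section counts children, and the analysis section counts samples with no allowance for clustering.

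*Protocol*

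**What the plan says.** **Consensus sequencing.** Protocol, Study methods, HIV DRM testing: each child is sequenced at the first VL of 1000 copies/mL or more, and children starting ART are also sequenced. "Subsequent samples from the same child on the same ART regimen will not be routinely retested". The precision statement in Section F matches this rule: "With 284 participants randomized to the intervention arm, we expect approx. 35% (100) to not achieve viral suppression" at the first test. It then gives exact 95% intervals for n=100.

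**NGS.** The same part of Study methods, on the extension: "All samples with VL $\geq$ 200 copies/ml will be tested by NGS". Over that period staff "only collect blood samples and administer questionnaires every 6 months up to 5 years of follow-up". The Procedures section says of the children that "they may be followed every 6 months up to 5 years by routine clinic staff for VL monitoring", with NGS again triggered at 200 copies/mL. Neither place limits NGS to one sample per child, viraemic episode or regimen.

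**Analysis.** Section F, Study Aim 2: "We will report the proportion of samples with each type of mutation detected by drug class". Risk factors are examined by logistic regression, with no term for repeated samples. Then: "The above analytic approaches will be taken for analyzing data from the NGS genotyping and phenotyping".

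**Outcome definition.** Protocol, Outcome Measure(s), Study Aim 2, describes the proportion of tested children who have significant mutations in each drug class, and applies the same approaches to NGS and phenotyping, with emerging dolutegravir resistance in mind.

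**SAP.** It follows children to 12 months and does not mention NGS. Its DRM outcomes are proportions of tests and samples, with plain logistic regression.

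**The concern.** When each child supplies one sequence per regimen, the share of samples and the share of children nearly coincide, and treating observations as independent is close to true. NGS removes the restriction that made this so. A child who stays viraemic can enter at several visits, and those sequences are likely to resemble one another.

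Two consequences follow if samples are the unit. The proportion describes viraemic samples and may be read as the share of children with resistance. Intervals and tests also treat repeats from one child as new information. Monitoring emerging dolutegravir resistance is the stated reason for the extension, so this is the figure its readers will look for.

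**Working it through.** **Step 1: the plan's own figure.** Section F takes 284 × 0.35 = 99.4, about 100 children with one sequence each. Its intervals are 71.3–87.0% for a prevalence of 80% and 5.1–17.1% for 10%. Treating 100 observations as independent:

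- Mid-P exact: 71.3–87.0% and 5.2–17.1%.
- Clopper–Pearson: 70.8–87.3% and 4.9–17.6%.

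The stated figures are reproduced to within 0.5 point. They are right for one sequence per child.

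**Step 2: the ceiling on repeats.** Six-monthly visits from month 12 to month 60 give (60 − 12) / 6 = 8 scheduled occasions after the primary endpoint. The documents do not say how many will be viraemic.

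**Step 3: standard errors.** Let m be the samples per child (taken as equal) and rho the within-child correlation. Both are assumptions. For a proportion, or a covariate constant within child:

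- design effect = 1 + (m − 1) × rho
- true SE / naive SE = √(design effect)
- approximate coverage of a nominal 95% interval = 2Φ(1.96 / √(design effect)) − 1

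| m | rho | Design effect | True SE / naive SE | Coverage |
|---|---|---|---|---|
| 2 | 0.3 | 1.3 | 1.14 | 91.4% |
| 2 | 0.5 | 1.5 | 1.22 | 89.0% |
| 2 | 0.9 | 1.9 | 1.38 | 84.5% |
| 8 | 0.3 | 3.1 | 1.76 | 73.4% |
| 8 | 0.9 | 7.3 | 2.70 | 53.2% |

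The rows with m = 8 are the extreme case in which every viraemic child is viraemic at every visit.

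As an example, take 100 viraemic children (borrowed from Step 1, not an NGS forecast) and a prevalence of 10%. With 2 samples each, the naive Clopper–Pearson interval on 200 samples is 6.2–15.0%. At rho = 0.5 the effective size is 200 / 1.5 = 133.3, and the interval is 5.5–16.4%.

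**Step 4: weighting.** Assume that 20 of 100 viraemic children have k samples each and the other 80 have one, with resistance 30% in the first group and 10% in the second. The per-child figure is (20 × 0.30 + 80 × 0.10) / 100 = 14.0%.

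- k = 2: (40 × 0.30 + 80 × 0.10) / 120 = 16.7% of samples.
- k = 8: (160 × 0.30 + 80 × 0.10) / 240 = 23.3% of samples. The 20 children supply 160 / 240 = 67% of them.

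If resistance is 10% in both groups, both figures are 10%. The estimate does not move, and only the interval is wrong.

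**The case against.** The strongest objection is that the Outcome Measure(s) section already counts children and carries that to NGS. That stands, and it means the documents conflict on the unit. It does not settle the matter, because it gives no rule for choosing or combining a child's samples and says nothing about the regression.

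Four further points limit the claim:

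- Section F names no unit for the logistic model. Many listed factors (sex, prior exposure, caregiver status, facility) would fit one row per child. What is shown is silence about repeats. An intention to ignore clustering is not shown.
- No interval is specified for NGS. The n=100 precision statement concerns consensus sequencing in the intervention arm, and part of the NGS work is descriptive.
- Consensus sequencing also permits a second sample, after a regimen change or outside routine practice. The contrast is one of degree.
- Repeats may be few. NGS needs a viraemic result in routine records and a usable or recalled sample, and dolutegravir has a high barrier to resistance. Against this, the Preliminary Studies section reports that only 23% of children with virologic failure and a follow-up test had suppressed. Those data come from 2014–2015 and say nothing about dolutegravir.

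A reader might also infer that every risk-factor p-value is anticonservative. The documents do not support that. Some listed factors, such as duration on ART, weight-for-age and immunological status, change within child, and ignoring clustering need not shrink their standard errors and can inflate them.

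**Conclusion.** The NGS analysis has no settled unit. The outcome section counts children, Section F counts samples, and no method for repeated samples is named. The 12-month SAP does not repair this.

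If Section F is followed as written, children with repeated viraemia are over-weighted, and standard errors are too small for proportions and for covariates fixed within child. The size cannot be derived from the documents. At an assumed 2 samples per child and correlation 0.5, coverage is about 89%. Over 2 to 8 samples and correlations of 0.3 to 0.9, it runs from about 91% down to 53%, with the lower end an extreme case.

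It is tempting to conclude that the reported resistance prevalence will be biased. The documents do not support that as a fact. It would require samples to be the unit and resistance to differ between repeatedly viraemic children and the rest. The Background section's argument, that adherence support cannot overcome multiple mutations, makes such a difference plausible, but no figure is given.

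The point is worth correcting because the remedy is nearly free. It does not touch the primary outcome.

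**What to change.** Reconcile the Outcome Measure(s) section with Section F, Study Aim 2, and add the following to the analysis plan for NGS and phenotyping:

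1. The child (or child-regimen) is the denominator for the main resistance proportions. Report two: resistance at the first viraemic sample, and cumulative detection per child over follow-up. The first alone would miss resistance that emerges later, which is what the extension is meant to detect.
2. Any per-sample proportion is labelled as such, with the number of children and samples shown and an interval that allows for clustering by child.
3. Any regression that includes more than one sample per child uses GEE or child-clustered robust standard errors. This corrects the standard errors but does not by itself give each child equal weight, so item 1 is still needed.

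The cost is a few sentences, slightly wider intervals and a little more analysis work. No new data are needed.

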Using a family model of care, FACES implements comprehensive pediatric HIV care and treatment services in accordance with the Kenyan MOH ART Guidelines. The latest guidelines, released in 2016, support initiation of ART for all individuals living with HIV, regardless of CD4 cell count or disease severity. Recommended 1st and 2nd line ART regimens are outlined in **Table 1**. Routine VL monitoring is offered through a laboratory network connected to a national, centralized laboratory and is recommended for children after six months of continuous ART and annually thereafter for those with VL <1000 copies/mL. Management of children with VL  $\geq$  1000 copies/mL includes adherence intensification and repeat of VL testing in three months followed by possible switch of ART for those who are still not virologically suppressed. Only those children on 2nd or 3rd line ART who continue to have viremia after adherence optimization, undergo DRM testing at a national reference laboratory. This testing process requires initial consultation with the Kenyan MOH HIV ART treatment committee, who then approves centralized DRM testing, receives the results, and eventually guides the local provider on management of the child failing their 2nd or 3rd line ART.

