OLA Simple-based DRM testing: We will evaluate the ability of OLA Simple to identify DRMs by comparing its results against DRM testing results from CS from study samples, as well as from the de-identified stored samples at the Kenya National HIV Reference Lab (NHRL), a key partner and stakeholder in future scale up of POC HIV DRM testing in Kenya. We will also evaluate the usability of OLA Simple when performed in the field in a clinical setting, bringing OLA Simple one step closer to being implemented as a POC DRM test. To increase efficiency, the OLA Simple testing will be conducted retrospectively, once the majority of samples to be tested have been collected, with direct observation from the [name] team. Nonetheless, to gain better insight into technician performance without direct supervision from the developers, we will also conduct a limited, prospective one-month long OLA testing towards the end of the participant follow-up. We will also partner with NHRL to cross-validate samples that have already undergone CS for clinical purposes and where leftover specimens are now stored and available for analysis at NHRL. These specimens are collected as part of routine clinical care from individuals experiencing viral failure, and are used for routine surveillance and evaluation of new test kits within the Kenya Ministry of Health. For NHRL, the use of their de-identified, stored specimens falls under the existing NASCOP-MOH routine lab validation procedures. Of note, results of the OLA Simple testing will not be returned to patients or providers, as this technology has not yet been approved for clinical use. The following procedures will be followed:

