The study is being conducted Kisumu County, western Kenya at low-resource, high-volume, high-HIV burden primary health care facilities. These government facilities are supported by the Ministry of Health (MOH), Kenya and HIV implementing partners funded by PEPFAR/CDC.

Comprehensive pediatric HIV care and treatment services are provided in accordance with the Kenyan MOH ART Guidelines. Children diagnosed with HIV are initiated on ART regardless of CD4 count per national guidelines. Routine VL monitoring is offered through a laboratory network connected to a national, centralized laboratory and is recommended for children after six months of continuous ART and every six months thereafter for those with VL <1000 copies/mL. Management of children with VL > 1000 copies/mL includes enhanced adherence counseling and repeat of VL testing in three months followed by possible switch of ART for those who are still not virologically suppressed. Only those children on 2nd or 3rd line ART who continue to have viremia after adherence optimization, undergo DRM testing at a national reference laboratory. This testing process requires

approval by the Kenyan MOH HIV ART treatment committee, who also guides the local provider on clinical management.

Study population

The study population was recruited from CLHIV ages 1-14 years newly initiating or already receiving ART at the study facilities. Infants <1 year of age were not included in the study as they frequently require more than 6 months of ART to suppress their initially high VL, and thus require specialized interpretation and management of VL results.

Eligibility criteria include:

- Children aged 1-14 years living with HIV (documented HIV positive or HIV VL)
- Already on ART or newly initiating ART

Randomization, allocation, and blinding

We randomized study participants 1:1 to the intervention vs. control arms using a blocked randomization scheme with varying block sizes, stratified by facility site and age groups (Group A: 1-9 or Group B: 10-14 years of age). Study staff ensured fidelity to the arm allocations by being the only ones able to order a POC VL. All investigators were blinded but participants, site coordinators, and the data team were not blinded to the randomization procedures.

Power calculations

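### OLA Simple predictive values have no split by specimen source, so read plainly they would describe an unstated mix of study samples and reference-laboratory specimens rather than study children with viraemia

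*Protocol*

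**What the plan says.** The Protocol's Study methods (OLA Simple-based DRM testing) compare OLA Simple with consensus sequencing on study samples, "as well as from the de-identified stored samples at the Kenya National HIV Reference Lab". The NHRL specimens are "samples that have already undergone CS for clinical purposes and where leftover specimens are now stored and available for analysis at NHRL", and were "collected as part of routine clinical care from individuals experiencing viral failure". No age limit, treatment line or number is given for them.

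Study samples are sequenced at a child's first viral load of 1000 copies/mL or more, and in children starting ART (Study methods, HIV DRM testing). About 100 intervention-arm samples are expected (Data Analysis Plan, Study Aim 2; SAP, Power calculations).

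On routine sequencing, the Protocol's Study Setting says that it is children on 2nd or 3rd line ART "who continue to have viremia after adherence optimization, undergo DRM testing at a national reference laboratory". The SAP's Study setting repeats this, and the Protocol's Background says the same of Kenya generally.

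The Aim 2b analysis reads "We will calculate sensitivity, specificity, and positive and negative predictive values for the detection of DRMs per codon", and the comparison is "stratified by retro- or prospective testing". No other stratum is named. The stated benchmark is sensitivity and specificity above 90%; PPV and NPV have none. The SAP contains no OLA Simple analysis.

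**The concern.** Sensitivity and specificity condition on true mutation status, so mutation prevalence does not enter them directly. PPV and NPV depend on it directly. If two populations with different codon prevalence are combined, the predictive values depend on how many specimens each supplied, which here is a matter of what the reference laboratory has in storage.

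PI codons are the most exposed. The named second-line regimens in Table 1 (Study Setting) contain a boosted PI, so later-line patients have usually had PI exposure. The 2013 survey found no PI mutations in viraemic children (Preliminary Studies), and the Background says the kit's PI codons have yet to be validated. A combined PPV could therefore look reassuring at the codons where least is known. Aim 2b is meant to support later clinical use of the assay, and predictive values are the figures a programme would most readily carry over to a child with viraemia.

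**Working it through.** The documents give no expected PPV or NPV, no NHRL count and no prevalence by source, so there is no planned figure to reproduce. The check is how far the predictive values move when only the specimen mix changes.

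**Formulas** (Se sensitivity, Sp specificity, p prevalence)
- PPV = Se·p / [Se·p + (1−Sp)(1−p)]
- NPV = Sp(1−p) / [Sp(1−p) + (1−Se)p]
- Pooled p = (100·p_study + m·p_NHRL) / (100 + m)

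**Inputs from the documents**
- 100 sequenced study samples.
- Se = Sp = 0.90, the edge of the benchmark.
- Se 95% and Sp 100% in initial testing (Background).
- K65R 4% and M184V 75% in the 2013 survey (Table 2, Preliminary Studies), used as study prevalences.

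**Assumptions, not in the documents**
- m = 50 to 200 NHRL specimens.
- PI codon: 2% in study samples, 10–30% in NHRL.
- K65R 10–20% and M184V 50–90% in NHRL.
- Se and Sp equal in both sources.

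**PI codon, Se = Sp = 0.90**
- Study samples only: 2 mutant, 98 wild-type. True positives 1.8, false positives 9.8. PPV = 1.8/11.6 = 15.5%; NPV = 88.2/88.4 = 99.8%.
- Smallest shift (m = 50 at 10%): 7 mutant, 143 wild-type. PPV = 6.3/20.6 = 31%; NPV 99.5%.
- Largest shift (m = 200 at 30%): 62 mutant, 238 wild-type, pooled prevalence 20.7%. PPV = 55.8/79.6 = 70%; NPV 97.2%.

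**Summary**

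| Codon, metric | Se/Sp | Study samples | Pooled |
|---|---|---|---|
| PI, PPV | 0.90/0.90 | 15.5% | 31–70% |
| PI, PPV | 0.95/0.99 (Sp assumed) | 66% | 82–96% |
| K65R, PPV | 0.90/0.90 | 27% | 37–61% |
| M184V, NPV | 0.90/0.90 | 75% | 61–87% |
| M184V, NPV | 0.95/1.00 | 87% | 78–93% |

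The M184V range straddles the study value: NPV rises if the codon is rarer in NHRL specimens and falls if it is commoner. At Sp = 1.00 the false-positive term vanishes, so PPV is 100% at any prevalence and only NPV moves.

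**The case against.** **Pooling is not stated.** The analysis paragraph does not mention NHRL, and Study methods introduces that work as a cross-validation with a partner laboratory, so separate reporting may be intended. This stands as a limit: combination is the plain reading of one evaluation with two sources and no source stratum, but it remains a reading. The one-month prospective stratum may contain study samples only, in which case the mixing falls mainly in the retrospective stratum.

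**Late-line enrichment is inferred.** Table 1 also sends children under 3 years, whose first line contains LPV/r, to national DRM referral, so the route is not purely later-line. Nor are study children a PI-free comparison group: enrolment is open to any child on ART, the survey's 0% came with infrequent PI use, and the Data Analysis Plan says PI mutations are increasing. All of this stands, and the 2% is only illustrative.

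**Initial specificity was 100%, so PPV would not move.** This is weak support. It comes from sixty dried blood spots plus an unstated number of previously sequenced samples. Even if all sixty were wild-type at a codon, the exact 95% lower limit is 0.025^(1/60) = 94%; with Se 95% and p = 2%, PPV is then 0.019/(0.019 + 0.0588) = 24%. The Background also says earlier testing covered only NRTI and NNRTI codons.

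**No decision in the plan rests on PPV or NPV.** Correct. Results are not returned to providers, and the benchmark uses sensitivity and specificity. This limits the point to the reporting of a validation aim.

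**Stronger readings.** A reader might infer that every resistance codon is enriched in NHRL, or that a PI codon could reach 30% in the pool. The documents support neither. From 2% in 100 study samples, a 30% pool needs NHRL prevalence of (60 − 2)/100 = 58% with 100 specimens, or (90 − 2)/200 = 44% with 200. For NRTI and NNRTI codons even the direction is unknown.

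**Conclusion.** The point holds in a limited form. As written, Aim 2b would give per-codon PPV and NPV that depend on an unstated mix of two populations, and nothing in the SAP repairs this. Such values would not describe study children with viraemia. PI-codon PPV would probably be inflated; under the stated assumptions, by a factor of about two (31/15.5) to four and a half (70/15.5) at 90% sensitivity and specificity, and by less at higher specificity. The true size cannot be given without NHRL numbers, treatment lines and ages.

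A reader might conclude that the OLA Simple validation as a whole is compromised. It is not: sensitivity and specificity do not depend directly on prevalence, and the NHRL specimens are useful for estimating them. The change is worth making because it is cheap and the affected figures are easily misapplied. It does not bear on the trial's primary outcome.

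**What to change.** In the Protocol's Data Analysis Plan (Study Aim 2, Aim 2b):

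1. Report sensitivity and specificity by specimen source (study or NHRL) as well as by retrospective or prospective testing, with the number, treatment line and age group of NHRL specimens where known.
2. Do not report PPV or NPV from the pooled specimens.
3. As the main result, derive PPV and NPV from estimated sensitivity and specificity at the codon prevalence observed in viraemic study participants. Aim 2a already plans to report the frequency of each mutation type in the intervention arm. Give confidence intervals that carry the sampling error of all three quantities.
4. Show PPV and NPV calculated directly in study samples as a supplement where there are enough positives.

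The cost is a few sentences, a source variable that should already be known for each specimen, and wider intervals. At a rare PI codon the widening is large. Direct values would rest on about 2 mutant samples in 100. The derived PPV is also imprecise: 2/100 has an exact 95% interval of 0.24% to 7.0%, which at Se = Sp = 0.90 puts PPV between about 2% and 41% before any error in Se or Sp. The derived version also assumes that sensitivity and specificity carry over between sources, which the by-source display in item 1 lets the reader judge.
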